**Abstract:**

The best match between any person with disability and the assistive technology (AT) only can be gotten through a complete assessment and a monitoring of the needs, abilities, priorities, difficult and limitations that he/she finds in his/her life. Without this analysis, may be the risk that the AT doesn't adapt to the expectation of the person. Like this, the user, in few time, could abandon the AT device, with the unnecessary spends of resources. Therefore, is important that any project focused in the development of new innovating AT for people with disabilities includes the perspective of outcome measures as an important phase of the research. In this sense, the incorporation of the assessment, implementation process and outcome measures is vital to get the transferability during the whole project and to get the general perspective from the final user.

The protocol presents a project that aims to improve the independence, participation and functional mobility of people with disabilities.

The sample is formed by people with disabilities that will participate from the first stage of the process, with an initial assessment of their abilities and needs, a complete implication during the test of technology, and in the final application of outcome measures instruments.

Only with this perspective and active participation of the users is possible to carry on a user-centered approach. That fact will allow to define and to generate technological solutions that really adjust to the expectations, needs and priorities of the people with disabilities, avoiding that the AT be abandoned, with the consequent health and social spending.

## 1. Introduction:

The present document is the description of a Subproject of a global and complete coordinated Project, in which are participants the University of A Coruña, the University of Alcalá de Henares and the University of Sevilla, and its title is: Artificial Intelligence and Robotic Assistive Technology devices for Disabled People (AIR4DP).

That coordinated project has the funding by the Ministry of Science, Innovation and Universities (government of Spain), through the call “Proyectos I+D+i 2019 – Retos de la Sociedad”, reference: PID2019-104323RB. The main expected result of this project is the implementation of assistive technology (AT) that allows to incorporate the last innovations in artificial intelligence and mobility to improve the quality of life (QoL) of people with disabilities.

The three subprojects that form part of the coordinated one are:

- Artificial Intelligence and Robotic Mobile Platforms to Improve Disabled People Independence (AIRPLANE): AIRPLANE is presented by the University of Alcalá (UAH). It aims to offer to the AIR4DP project advanced mobile technology solutions to improve the independence of people with functional diversity. The platforms are able to autonomously navigate the environment, e.g., the house of the user with functional diversity, and track the activity of the people, anticipating dangerous situations, such as a fall or an awkward interaction with a household appliance.
- Augmentative Affective Interface (AAI): Searches for a better human-robot experience by including remote monitoring and local wearable sensors to collect the subject's physiological data for both emotional state detection and activity recognition. Namely, AAI looks for improving the quality of life of people with disabilities by adapting and promoting physical activity autonomously but in a controlled scenario.
- Assessment and counseling to get the best efficiency and effectiveness of the Assistive Technology (MATCH): That subproject is the complement to get the best evidence about the impact of assistive technology based on AI in the life of a person with a disability. The perfect match between person and technology can only be achieved through a complete assessment and monitor of the capabilities, needs, priorities, difficulties, and limitations that a person has in their life. Without these analyses, there is a risk that the technology does not adapt to the expectations of the person. The person in a short time abandons the project with the result of unnecessary expenditure of resources. So, it is relevant that within the coordinated project, a team with experience in evaluation, design, and outcome measures of assistive technology for people with disabilities is integrated in the consortium.

The main result of the AIR4DP project consists in the implementation of assistive technology that allows us to incorporate the latest advances in AI to improve life quality of people with disabilities. With this target, we present a coordinated project that is divided into three sub-projects, whose main goals consist in developing and evaluating the breakthrough of the proposed technology in the people with functional diversity. In a nutshell, AIR4DP main scientific objectives are:

1. Create novel mobile platforms with advanced perception, interaction and navigation capabilities, able to stimulate and monitor the improvement of the independence of people with functional diversity (SUBPROJECT 1: AIRPLANE).

2. Develop new wearable technical solutions for monitoring physiological aspects to help the detection of emotional states and user activities (SUBPROJECT 2: AAI).
3. Get the best evidence about the impact of assistive technology based on AI in the life of the person with a disability (SUBPROJECT 3: MATCH).

The consortium formed allows us to cover from the implementation of intelligent mobile platforms to improve independence (UAH) and multi-modal wearable sensor solutions for monitoring people (US), to the assessment, from a health point of view, of the impact of these aids on people with functional diversity (UDC, UAH).

In this Study Protocol the justification and the development of subproject MATCH is explained. It will be coordinated by the University of A Coruña, and its performance implies the participation of people with disabilities.

## **2. Background:**

Assistive Technology (AT) is an umbrella's concept that refers to devices with different levels of technological complexity. AT improve the functional capacity in different areas of a person's life. Some of those areas are: a) eating (for example, adapted cutlery, dishes with flange); b) mobility (for example, powered wheelchairs, walkers, canes); c) communication (for example, augmentative and alternative communication systems); d) access to the computer (for example, screen readers, adaptations for keyboards, push buttons, computer systems, switch); e) housing; f) transport; and g) leisure or sports (1). Therefore, the AT are devices that facilitate and/or allow the development of activities of a person with a disability.

However, despite the clear benefits of the use of assistive technology devices (ATD) in the life of people with disabilities, it has also been associated with some problems. The more common ones can be grouped into several categories: lack of information about available ATD, economic factors related to the high price of products, forms of access to support products, as well as factors related to the guarantee, maintenance and insurance of the ATD (2-4).

One of the most frequent and influential factors during the process of prescription and subsequent use of the ATD, is the lack of matching between the person and the recommended ATD (5,6). This problem may lead to the abandonment or non-use of the ATD. The non-use of devices has clear causes and obvious consequences not only on the quality of life and the autonomy of the person with disability but also cost-benefit effects (7). To achieve an increase in the successful use of ATD and, therefore, to reduce the probability of being abandoned or not fulfilling its initial function, it is essential to carry out an adequate assessment of the user's needs with reliable measurement tools to improve decision making for the prescription and adaptations of ATD.

The outcome measure is a set of considerations and tools to determine if a service, product or device allows achieving the goals for which it has been created, under criteria of efficacy, and effectiveness. In other words, outcome measures are the evaluation process in the provisioning service that is designed to quantify and establish a baseline on something that works (its effectiveness), the group on which it works, and what level of economic efficiency it provides (8). So, professionals prescribing AT have to take into account the need for applying outcome measures to improve their intervention, with a process evidence-based.

WHO General Assembly in 2018 published a resolution on the importance of ATD and services globally (including assessment) and supported the position papers. The main considerations that

have to take into account the governments in the provision of assistive technology to all citizens are related to Personal, Products, Provision, and Policy (9). To give support to the professionals, to improve the services of AT and to benefit the final users of those devices, several models of outcome measures have emerged (6,10). Those models indicated the main factors to take into account in the process of getting a match between the person and assistive technology:

- The functional problems that ATD intends to solve.
- The characteristics of final users and their needs and priorities.
- The characteristics of the device that are responsible for its intervention.
- The context in which ATD is applied or used.
- The expected changes in the state of a user and its context are the results, both short and long term.
- The impact of AT devices on the individual's participation in the environment.

A revision done by the ATOMs Project identified 22 models of outcome measures related to ATD, and 14 tools or instruments to assess the results of that device, such as, psychosocial impact of ATD in the quality of life, satisfaction with the ATD or level of matching between person and technology (11). In Spain, the research related to outcome measures in ATD is deficient, because there are not many specific measurement instruments that are validated in the Spanish population. The application of these tools was published only in two research projects (12,13). The PhD thesis of the principal investigator ([name]) of the MATCH subproject and all the research after that is the only available expertise in that topic (7,14–16).

Therefore, the third subproject of this proposal is focused on the implementation of outcome measurement tools to improve the efficacy, effectiveness and the real utility of the ATD developed. On the other hand, it is also very important to assess the functional impact the ATD has on user's participation in their social environment. For that, other measurement tools to assess functional mobility outcomes will also be also carried out during basal assessment and after 6 months of ATD implementation. The mentioned tools include (all in their Spanish adapted version) the Six-minute Walk Test (17,18), 10 Meter Walk Test (19), Pediatric Balance Scale (20), and the Functional Independence Measure (FIM) (21,22). The measurement tools will be carried out depending on the characteristics of the ATD and the targeted population.

### 3. Objectives and initial hypothesis

The global project is a multi-disciplinary and cross-border research, where the **main research objective consists in the development of novel AI and computer vision based robotic solutions with advanced mobility and human-robot wearable interaction capabilities, to improve the independence and stimulation of people with disabilities.**

The general objective of this project is based on the hypothesis that the application of Information and Communication Technologies (ICTs) and AI can improve the quality of life and independence in the group of people with disability by providing support platforms to enhance the participation in activities of daily life and in their communities.

Overall, with the coordinated research we will address the following open questions:

- What techniques can be proposed from the perspective of artificial intelligence and computer vision to provide effective solutions for people with functional diversity?
- What are the challenges posed by human-robot interaction, using accompaniment platforms and wearable devices, with people with disabilities?
- How should we approach evaluation and consultancy for the design of robotic solutions as assistive technologies, so that we can guarantee an efficient and correct matching between person and technology?

In concrete, for this study protocol, the second hypothesis is related to the relevance of the assessment of the interaction between the users and the AT: in order to guarantee a high match person-AT, to also get a positive psychosocial impact in the life of people with disabilities, the assessment and monitoring result two fundamental aspects.

According to this hypothesis, the research groups has fixed two main objectives for the MATCH subproject:

- To determine the psychosocial impact of AT created during the coordinated project (AIR4ALL) on the life of people with disabilities.
- To promote the best match between the user and the assistive technology used.

To complete, few secondary goals have been proposed:

- To assess the functional skills and abilities of people with disabilities, and to identify their needs to get independence in mobility and activities of daily living.
- To design and create the best technology solutions individualized for each person, meeting with the design for all principles, and promoting the involvement of the final user.
- To validate the assistive technology's solutions designed and prototyped in order to increase the levels of participation in daily activities to people with disabilities.
- To validate a protocol/model of outcome measures in the field of assistive technology to increase the efficiency and effectively of selecting and prescribing these products.

#### **4. Methodology**

**Design:** Pilot study: Prospective, longitudinal and analytical cohort

**Environment of study:**

The project will be done by researchers of Universities of Alcalá de Henares, Sevilla and A Coruña. So, the context of study is restricted to that locations.

In the case of University of Alcalá de Henares, the context is located to this city and few districts of Madrid. The centers of people with disabilities that will be able to participate are: Centro de Atención Integral SAIDI-APHISA, Fundación ASTOR, Colegio Público de Educación Infantil y Primaria (CEIP) Luis Vives, Colegio Público de Educación Especial Pablo Picasso and ATENPACE.

The University of Sevilla will carry on the project in the city of Sevilla and its metropolitan area. The collaborators centers will be: ASPACE Sevilla and Colegio de Educación Especial Directora Mercedes Sanromá.

Finally, in the case of University of A Coruña, its context of study includes the metropolitan area of A Coruña and Santiago de Compostela, conditioned by the influence area of its collaborators: ASPACE Coruña and Confederación Gallega de Personas con Discapacidad (COGAMI).

**Period of study:**

The coordinated project has a duration of 36 months, and it has been programmed from the month of July 2020 to the month of April of 2023.

**Sample and selection of participants:**

The participants will be those that meet with the inclusion criteria and not the exclusion ones, and they will have given their informed consent to participate in the research.

*The inclusion criteria are the following:*

- People with recognized disability, derived by a disease or a permanent health status.
- Age between 2 and 21 years old.
- To form part of any of collaborators centers with the three universities.
- To have an independent functional level moderate – low (assessed by the Functional Independence Measure).
- To have functional skills – mobility domain level moderate – low (assessed by the Spanish version of Pediatric of Disability Inventory – PEDI)

*The exclusion criteria are:*

- To have any health status that is incompatible with the use of assistive technology designed and prototyped in the project.
- To have cognitive skills very limited, that limits to follow the instructions to good use of AT.
- Not to have adequate human supports to make use of AT.
- To have functional skills – mobility domain level low (assessed by the Spanish version of Pediatric of Disability Inventory – PEDI), with the need for maximum assistance from caregivers.

The research group have also fixed *criteria for retirement* of study's participants:

- Voluntary abandonment of the research and/or to finish the relationship with the center where the research project is carrying on.

**Selection of participants:**

All persons that meet with inclusion criteria will be invited to participate in the research. The selection of participants will be done by each research group (UAH, US and UDC), through their contact with collaborators centers (specified below). In all cases, an information letter with the whole information of the project will be done to the chief or directors of those centers, to get the authorization to implement the research project in that entity.

**Variables and Instruments:**

The study variables and the measure instruments correspondent are specified in Table 1.

The use and the application of each instrument is conditioned by the stage of intervention process, that is defined and described in the next section. All instruments have been translated and validated into the Spanish context.

The access to the clinic history of the participants won't be required to the performance of this project.

Nevertheless, all obtained results will be codified and manage through the **REDAP Platform**, that allows the capture of electronic data in the design of research database

**Procedure:**

The performance of MATCH subproject will be conditioned by the advance of other two subprojects. Nevertheless, in the schedule (see below) is showed how the different tasks are related to each other, and how the development of the complete project will be in the timeline.

The tasks that will be done in the MATCH subproject contemplates several consecutive phases:

1. Planning of assessment process: The research group defines the study variables and measure instruments to obtain the data. Those tools will allow to determine the needs, capabilities, priorities and expectations of participants, with respect to the use of AT.
2. Contact with the collaborators centers and presentation of the project: The members of each research group will contact with the collaborators centers (specified in sections before) to present the characteristics of the project, to get its authorization and, at the time, to give all information of the users, potential participants.
3. Selection of participants and process of informed consent: According to the inclusion criteria, the participants will be recruitment of each collaborator center, and the information form will be given to them. After the reading, participants will offer their informed consent to involve in the research.
4. Initial assessment: In this phase the evaluation of the participants will be done, with the application of the instrument presented in table 1. According to the age of the person, specific questionnaires will be used to gather information more concrete about the skills for mobility. This assessment will allow determining the specific needs, demands and capabilities of participants. The assessment process will be done by professionals of research group in rooms of collaborators centers.
5. Technical advice to the development of the other subprojects (AIRPLANE and AAI): According to the obtained results from initial assessment and after the analysis of first data, the research group of UDC will inform to the groups of UAH and US the main findings. That data will be taken into account and incorporated to the technical development of the AT. Only in this way, it will generate viable and adequate products to the detected needs previously, and this assistive technology that integrates the robotic and AI models answer correctly to these demands.
6. Check of functioning and adaptation of assistive technology to the requirements of people with disabilities: The research group of UDC will verify the components of assistive technology in terms of usability and universal design, and its adequacy to the specifications identified in the previous phase. That process will be a collaborative task, in which will participate the members of research group and the professionals of collaborator centers, not implicating a direct intervention with the users.

7. Implementation of AT in the daily life of participants: The professionals of collaborator centers, supported by the research groups, will carry on the training in the use of AT by the participants, facilitating its incorporation during the performance of activities of daily living.
8. Determination of possible improvements in the assistive technology, derived by the experience of participants: The members of research group will test the AT in the context of people with disabilities, detecting and registering the possible lacks and improvements that the device would need to get the best match between the AT and the user.
9. Application of outcome measures and analysis of the data: After the process of implementation of AT (the next 2 and 6 months), members of research group and the professionals of collaborators centers will apply the measure instruments to determine the possible improvements in the level of functional independence (FIM scale) of people with disabilities, the impact that the AT has had on their lives (PIADS scale) and the level of matching between person and AT (ATD PA – MPT model). The data will be analysed in descriptive and inferential terms, establishing the respective comparison with the obtained results of initial assessment.
10. Elaboration of explicative model or protocol: The obtained results from the use of AT by the participants, and its posterior analysis will allow to determine the influent factors that would be able to facilitate or restrict the good and efficient use of this device. That will be the best solution to demonstrate the efficacy and efficiency of AIR4ALL and its final goal to improve the participation and quality of life of people with disabilities.

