**Data analysis:**

The quantitative variables will be expressed as Mean (M) and Standard Deviation (SD), including range, minimum and maximum values. Apart from the simple description of data and variables, inferential analysis will be done to determine possible significant relationships and correlations between study variables or that allows to the contrast of hypothesis.

Shapiro Wilk and/or Kolmogorov – Smirnov will be applied to determine if the sample meets with the normal distribution criteria, and to decide the type of statistical test that will be implemented (parametric or no-parametric).

The T- student paired test or the U-Mann Whitney will be applied to establish the possible differences of means, according different dicotomic variables, in the assessment scales of FIM, PIADS, Walk tests and level of matching person – AT. The ANOVA test or Kruskal – Wallis will be used in the cases of polycotomic variables, to establish possible differences of means between results of the scales.

The association of numeric variables will be analysed by Pearson or Spearman correlation test, according to distribution of the sample. To evaluate the association of categorical variables, chi-square will be applied, or likelihood ratio if the observed frequencies are lower than 5%.

To check the differences between related samples, with repeated measures (in the case of FIM scale and the scales of mobility – initial assessment and in the follow-up of 2 and 6 months), the t-student test or the Wilcoxon ranges will be used, according correspond to the sample distribution.

The analysis of the data will be done with the program SPSS v.24 for Windows. The level of significance to do the contrast of hypothesis is established to 5%.

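### FIM may be scored by a wider pool of raters at follow-up than at baseline, including the staff who train participants, so a rater difference could enter the before-after change

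*Protocol*

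**What the plan says.** All of this is in section 4 of the Protocol.

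- **Baseline (Procedure, phase 4).** One group assesses: "The assessment process will be done by professionals of research group in rooms of collaborators centers".
- **Training (Procedure, phase 7).** "The professionals of collaborator centers, supported by the research groups, will carry on the training in the use of AT by the participants".
- **Device testing (Procedure, phase 8).** "The members of research group will test the AT in the context of people with disabilities".
- **Follow-up at 2 and 6 months (Procedure, phase 9).** Two groups assess: "members of research group and the professionals of collaborators centers will apply the measure instruments". FIM, PIADS and the person-technology matching measure are named there. The analysis is then described as "establishing the respective comparison with the obtained results of initial assessment".
- **Analysis (Data analysis).** A t-test or Wilcoxon test for related samples is applied to the repeated measures, "in the case of FIM scale and the scales of mobility". No rater term is mentioned.
- **Design.** "Pilot study: Prospective, longitudinal and analytical cohort". No comparison group is described.
- **Database (Variables and Instruments).** "all obtained results will be codified and manage" through an electronic data-capture platform. The text does not mention recording who made each assessment.

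**The concern.** The plan sets one assessor rule for baseline and a wider one for follow-up, then subtracts the first score from the second. In a controlled study, a shift in rating standards that affected both arms alike would largely cancel. In a single cohort it does not, and becomes part of the before-after change.

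The group added at follow-up is also the group that trains participants to use the device. Staff could then rate the functional independence of someone they have trained, which is an avoidable source of optimistic scoring. Scoring could equally be stricter, and that would hide a benefit. If nobody records who scored, the two explanations cannot be separated afterwards.

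What is at stake is the FIM change and, to a lesser degree, any other scale that depends on an assessor's judgement, such as the Pediatric Balance Scale where it is used (section 2).

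**Working it through.** **Reading the phases together**

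| | Baseline | Follow-up |
|---|---|---|
| Who assesses | Research-group professionals (phase 4) | Research-group members and centre professionals (phase 9) |
| Role of the added group | – | Delivers device training (phase 7) |
| Who scores FIM | Research group | Not stated |
| Use in analysis | Reference value | Paired comparison with baseline |

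Phase 9 is a collective sentence. It could mean joint scoring, instruments divided between the groups, or participants divided between them. The concern applies fully to the last reading. It also applies if instruments are divided and FIM goes to centre staff.

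**Size of the effect: illustration only**

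The Protocol states no sample size, SD, correlation or rater difference, so there is no figure of its own to reproduce. Its only usable input is the 5% significance level. Everything else below is assumed.

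- Units: baseline SDs of FIM, with equal SDs at both visits.
- Correlation between visits ρ = 0.8, so SD of change = √(2(1−ρ)) = √0.4 = 0.632.
- Gap g: centre-staff score minus research-group score for the same participant.
- Share f: proportion of participants whose follow-up FIM is scored by centre staff.
- True change zero; two-sided paired t-test.

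Mean apparent change = f × g. For n = 30, f = 0.5 and g = 0.2:

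- mean = 0.5 × 0.2 = 0.10
- variance of change = 0.4 + f(1−f)g² = 0.4 + 0.25 × 0.04 = 0.41, so SD = 0.640
- expected test statistic ≈ 0.10 / (0.640/√30) = 0.86
- probability of rejection by simulation: 13%

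False-positive rates with zero true change and ρ = 0.8:

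| n | Scored by centre staff | g = 0.1 | g = 0.2 | g = 0.4 |
|---|---|---|---|---|
| 16 | half | 6% | 9% | 19% |
| 30 | half | 7% | 13% | 35% |
| 60 | half | 9% | 22% | 64% |
| 30 | 8 of 30 | 5% | 7% | 13% |
| 30 | all (upper bound) | 13% | 39% | 92% |
| 30 | none | 5% | 5% | 5% |

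For n = 30, half scored and g = 0.2, the rate is 9% at ρ = 0.6 and 21% at ρ = 0.9.

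**A gap in the other direction.** With a true gain of 0.2 SD, n = 30, ρ = 0.8 and half scored by centre staff, power is 39% with no gap, 24% with g = −0.1 and 13% with g = −0.2.

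**What recording the rater would give** (n = 30 split 15/15, ρ = 0.8)

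- Standard error of the gap = 0.632 × √(2/15) = 0.231. The 95% half-width is 2.048 × 0.231 = 0.47 SD (0.67 at ρ = 0.6; 0.33 at ρ = 0.9).
- Half-width of the FIM change in the 15 scored by the research group throughout: 2.145 × 0.632/√15 = 0.35 SD.
- Half-width of the FIM change if all 30 are scored from one pool: 2.045 × 0.632/√30 = 0.24 SD.

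Recording alone therefore estimates the gap only roughly. Keeping one rater pool from the start gives the better precision.

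**The case against.** The strongest reply is that no harm is demonstrated. Phase 9 does not say that centre staff score FIM, or that they score it alone. Under joint scoring, or if they apply only other instruments, the problem shrinks or disappears. Even on the unfavourable reading it needs a rater difference that nobody has shown. Rater rules may also sit in Table 1, which is not in the text available, or in the assessment protocol listed as T1 in section 6. Silence about a rater field means little in a one-sentence description of the database. The figures show only that an assumed bias biases a test.

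Most of this is fair, which is why the point is stated conditionally and the figures cannot show that a problem exists. What survives is that phases 4 and 9 themselves assign assessors, and do so differently, with trainers added only at follow-up. The ambiguity is itself the thing to resolve. Assigning assessors is a matter of study conduct, not a detail left to an analysis plan.

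Three limits also stand:

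- FIM change is in neither main objective, and the study is a pilot.
- The reach beyond FIM is not settled. Phase 9 compares the data in general with baseline, while Data analysis lists only FIM and the mobility scales as repeated measures. The Pediatric Balance Scale is conditional, and section 2 names no assessor for it.
- The fix does not make raters independent. The research groups support training, test the device and belong to the consortium that develops it.

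**Conclusion.** The concern holds as a conditional one. The plan permits the rater pool to change between baseline and follow-up, brings in the trainers at follow-up, does not say who scores FIM, and has no comparison group that could absorb a rater shift. If centre staff score a share f of participants with a gap g, the FIM change is biased by f × g. On the assumed inputs this ranges from nothing (no FIM scored by centre staff) to an error rate of 92% (all scored, gap 0.4 SD, n = 30). At small gaps, small n or a small share it stays near the nominal 5%. The documents do not show which case applies.

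The main objectives, psychosocial impact and person-technology match, are largely unaffected, because PIADS and the matching measure are not among the repeated measures listed under Data analysis. This is a worthwhile, low-cost improvement to a secondary comparison and not a threat to the study. Confidence is medium, because Table 1 and T1 could already allocate raters.

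**What to change.** 1. In phase 9, state that FIM, and assessor-rated scales such as the Pediatric Balance Scale where used, are scored at follow-up from the same research-group pool as in phase 4. Use the same rater where feasible, and never the person who trained that participant.
2. Record rater identity at every visit in the study database.
3. Repeat the FIM analysis in participants scored by the same rater, or the same rater group, throughout. If the rule in step 1 is always kept, the rater-group version adds nothing; it matters when there are departures.
4. If Table 1 or T1 already allocates raters, bring phase 9 into line with it.

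The cost is a wording change and one database field; the staff are already named in phase 9. The downside is less flexible scheduling and some extra research-group time at follow-up across the three study areas, which the Protocol does not allow to be sized.

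This provides rater consistency, not blinding. It also leaves growth and time effects in place: participants are aged 2 to 21, and baseline precedes development of the device.
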